8.13.1.6 Anxiety Depression and Mood Scale (ADAMS)

The ADAMS (Anxiety, Depression, and Mood Scale) is a 28-item behavior-based informant instrument rated by the parent/caregiver and designed to assess anxiety, depression and mood disorders in individuals with intellectual disability. ¹⁹ Items are rated on a scale of 0 ("behavior has not occurred, or is not a problem") to 3 ("behavior occurs a lot, or is a severe problem"). The scale is composed of 5 factors which address: Manic/Hyperactive Behavior, Depressed Mood, Social Avoidance, General Anxiety and Obsessive/Compulsive Behavior. A caregiver identified upon enrollment of subject should have intimate knowledge of the subject's situation and level of impairment to be able to provide accurate information as required to complete the ADAMS. The caregiver completing the assessment should remain the same at all applicable visits throughout the trial.

8.13.1.7 Vineland-3 Rating Scale

The Vineland Adaptive Behavior Scales, Third Edition (Vineland-3)²⁰ assesses adaptive behavior in five domains, each with subdomains. The following three domains will be assessed in this study, as most applicable to the FXS population:

- 1. Communication
 - o Subdomains: Receptive, Expressive, Written
- 2. Daily Living Skills
 - Subdomains: Personal, Domestic, Community
- 3. Socialization
 - o Subdomains: Interpersonal Relationships, Play and Leisure, Coping Skills

The Vineland-3 will be administered as a standardized interview to a parent/caregiver by trained study staff trained and authorized to perform the interview. The Vineland-3 must be administered by the same rater for a given subject at all applicable visits throughout the trial. The caregiver completing the assessment with the study staff member should also remain the same at all applicable visits throughout the trial. If the site has performed a Vineland-3 assessment on the subject in the 6 months prior to screening, the results of that assessment may be used for the baseline (Day 1) assessment in this study.

8.13.1.8 Event-Related Potentials (ERP)

Event-Related Potentials (ERPs) enable extraction of neural responses associated with specific sensory, cognitive, or motor events from an overall EEG. ^{21,22}Auditory stimuli are presented and EEG events assessed in relation to timing of the stimuli. For this study, an ERP protocol developed to measure auditory habituation to trains of repeated stimuli, resting state delta power, and CHIRP responses in FXS will be used. ²³ This protocol has shown feasibility and clinical validity based on comparison to sensory hypersensitivity on the Sensory Profile in FXS. The EEGs will be read by who developed the protocol and has extensive experience in ERP evaluation.

Protocol: BPN14770-CNS-203 Tetra Discovery Partners, Inc.
Date: 25 June 2018 Confidential

8.13.1.9 Eye Tracking

Eye tracking has been successfully used to assess social gaze in FXS.²⁴ Testing will be conducted in a quiet room with the lights turned off. The eye tracker (Tobii) will be calibrated for each subject at the beginning of each session. Following calibration, subjects will view pictures shown on the screen. Each assessment begins with presentation of a scrambled face image for 1 s followed immediately by its matched face image for 3 s. An inter-trial interval (ITI) containing a uniform grey screen is shown for 0.5, 1, or 2 s, randomly determined. The order of face presentation is pseudorandomized and each eye tracking session lasts approximately 6 min. Measurements include looking time to the eye region of interest (ROI), and number of fixations to the eye ROI, as well as pupil dilatation by pupilometry. These measurements have been shown to have good test-retest reproducibility. All measurements are analyzed offline by a trained specialist.

8.13.2 Timing of Efficacy Assessments

8.13.2.1 Baseline (Period 1/Day 1)

The following exploratory efficacy assessments will be performed at Baseline (Period 1/ Day 1, prior to randomization):

- NIH Toolbox Cognitive Battery for Intellectual Disabilities (NIH-TCB)
- Test of Attentional Performance (KiTAP)
- Clinical Global Impression Severity Investigator rated (CGI-S)
- VAS Rating Scale using patient-specific behavioral anchors
- Aberrant Behavior Checklist (ABC)
- Anxiety, Depression, and Mood Scale (ADAMS)
- Vineland-3 Rating Scale
- Event-Related Potentials (ERP)
- Eye Tracking

8.13.2.2 Week 6 (Periods 1 and 2)

The following cognitive tests will be assessed at Week 6 during each Period:

- NIH Toolbox Cognitive Battery for Intellectual Disabilities (NIH-TCB)
- Test of Attentional Performance (KiTAP)
- Clinical Global Impression Severity Investigator rated (CGI-S)
- Clinical Global Impression Improvement Investigator rated (CGI-I)
- Visual Analog Scale (VAS) assessment of patient-specific behavioral anchors)

8.13.2.3 Week 12 (Periods 1 and 2)

The full battery of cognitive tests will be performed at Week 12 during each Period:

- NIH Toolbox Cognitive Battery for Intellectual Disabilities (NIH-TCB)
- Test of Attentional Performance (KiTAP)
- Clinical Global Impression Severity Investigator rated (CGI-S)

- Clinical Global Impression Improvement Investigator rated (CGI-I)
- Visual Analog Scale (VAS) assessment of patient-specific behavioral anchors
- Aberrant Behavior Checklist (ABC)
- Anxiety, Depression, and Mood Scale (ADAMS)
- Event-Related Potentials (ERP)
- Eye Tracking
- Vineland-3 Rating Scale

8.14 Pharmacokinetic Assessment

8.14.1 Plasma Pharmacokinetic Samples

Blood samples for BPN14770 concentrations will be drawn at screening and during the clinic visit at Week12 during each Period. Samples will be drawn at the time of the clinic visit, with documentation of time of day testing was performed, and time of day of most recent dose of study medication.

Pharmacokinetic samples will be retained and may also be utilized subsequently for biomarker assessment. Blood samples $(1 \times 4 \text{ mL})$ will be collected in Vacutainer tubes containing K_2 -EDTA as a preservative.

8.14.2 Processing and Shipment of Pharmacokinetic Samples

Blood samples will be kept on wet ice from the time of collection and throughout processing until frozen.

Blood samples will be centrifuged at 1500 x g (gravity) for 10 minutes at 4°C. The resulting plasma samples will be harvested and transferred into appropriately labeled polypropylene screw-cap tubes. Pharmacokinetic samples will be placed in a freezer at -80°C within 60 minutes of the blood draw. Samples will remain frozen until assayed. A more detailed description of plasma sample preparation requirements may be provided by the analytical laboratory and will supersede those provided in this protocol. Appropriate documentation will be placed in the study master file at the Clinical Site.

The samples will be transferred to the analytical laboratory after completion of the study or at mutually agreed upon time points during the clinical conduct of the study. Prior to shipment, the samples will be appropriately packed in a Styrofoam cooler containing dry ice. Sufficient dry ice will be added to ensure that the samples will remain frozen for at least 72 hours for remote shipments. The shipment will be accompanied by documentation containing the following information: name of the study drug product, protocol number, number of subjects, and number of samples included in the shipment.

All frozen pharmacokinetic samples will be transferred with accompanying documentation to:

Senior Research Analyst/Investigator CMIC, Inc. [name] [contact]

Pharmacokinetic samples at CMIC, Inc. will be stored in a freezer at -80°C.

8.14.3 Analytical Method

Plasma samples will be analyzed for BPN14770 using a validated assay.²⁵

Samples will only be analyzed for subjects whose treatment included administration of BPN14770. Samples will not be analyzed when matching placebo for BPN14770 was administered.

8.14.4 Plasma Pharmacokinetic Parameters

BPN14770 plasma levels will be presented in tabular form by Period at Week 12, and a listing of all subjects' data will be provided.

8.15 Biomarker Assessments

Biomarker samples will be collected concurrently with the pharmacokinetic samples at screening and at the Week 12 visits at the end of each Period. Samples will be processed in the same manner as the pharmacokinetic samples (see Section 8.14.2). Biomarker samples will be shipped to the sponsor for analysis.

9 EVALUATION AND REPORTING OF ADVERSE EVENTS

9.1 Adverse Events

An adverse event is defined as any untoward medical occurrence in a clinical investigation subject administered a pharmaceutical product, which does not necessarily have a causal relationship with this treatment. An adverse event can therefore be any unfavorable and/or unintended sign (including an abnormal laboratory finding), symptom, or disease temporally associated with the use of an investigational medicinal product, whether or not related to the investigational medicinal product. All adverse events, including observed or volunteered problems, complaints, or symptoms, are to be recorded on the appropriate CRF.

Adverse events, which include abnormal and clinically significant clinical laboratory test variables, will be monitored and documented from the time of first dose until study participation is complete (the Follow-up Visit). Subjects should be instructed to report any adverse event that they experience to the Investigator. Any medical condition already present prior to the subject taking the first dose of study treatment will be reported in the medical history. Should any changes in the subject's health occur between consent and first dose of study treatment, , the Investigator will make corresponding updates to medical history.

Beginning with the first dose of study drug, the Investigator will make an assessment for adverse events at each visit and record all adverse events, non-serious and serious, on the appropriate adverse event CRF. Any pre-existing medical condition or signs or symptoms that change adversely in severity, frequency, or seriousness (outside of the range of typical variation of the symptom over time in the past for the patient) after the subject takes the first dose of study drug and through the Follow-up Visit should be reported as an adverse event.

Wherever possible, a specific disease or syndrome rather than individual associated signs and symptoms should be identified by the Investigator and recorded on the CRF. However, if an observed or reported sign or symptom is not considered a component of a specific disease or syndrome by the Investigator, it should be recorded as a separate adverse event on the CRF. Additionally, the condition that led to a medical or surgical procedure (e.g., surgery, endoscopy, tooth extraction, or transfusion) should be recorded as an adverse event, not the procedure. Concomitant procedures should be recorded as such on the appropriate CRF.

Clinically significant abnormal laboratory values or other examinations (e.g., ECG) that are detected after the first dose of study drug and worsen during the study should be reported as adverse events. An abnormal laboratory result that is not verified by repeat testing does not necessitate reporting as an adverse event. The Investigator will exercise his or her medical, scientific, and clinical judgment in deciding whether an abnormal laboratory finding or other abnormal assessment is clinically significant. Clinically significant abnormal laboratory values occurring during the clinical study will be followed until repeat tests return to normal, stabilize, or are no longer clinically significant. Any abnormal test that is determined to be an error does not require reporting as an adverse event.

Treatment of any adverse reactions will be evaluated and managed by a physician.

9.2 Definitions

9.2.1 Adverse Drug Reaction

For adverse events with a causal relationship to study drug, follow-up by the Investigator will be required until the event or its sequelae resolve or stabilize to a level acceptable to the Investigator.

9.2.2 Unexpected Adverse Event/ Unexpected Adverse Drug Reaction

An unexpected AE/unexpected suspected adverse reaction is an AE or suspected adverse reaction that is not listed in the Investigator Brochure or is not listed at the specificity or severity that has been observed; or, if an Investigator Brochure is not required or available, is not consistent with the risk information described in the general investigational plan or elsewhere in the current application, as amended.

9.2.3 Serious Adverse Events

An adverse event or adverse reaction is considered serious if, in the view of either the Investigator or Sponsor, it results in any of the following outcomes:

- Death;
- A life-threatening adverse event;
- NOTE: An adverse event or adverse reaction is considered "life-threatening" if, in view of either the Investigator or Sponsor, its occurrence places the subject at immediate risk of death. It does not include an event that, had it occurred in a more severe form, might have caused death.

Protocol: BPN14770-CNS-203 Tetra Discovery Partners, Inc.
Date: 25 June 2018 Confidential

• Requires hospitalization or prolongation of existing hospitalizations; NOTE: Any hospital admission with at least one overnight stay will be considered an inpatient hospitalization. An emergency room visit without hospital admission will not be recorded as a SAE under this criterion, nor will hospitalization for a procedure scheduled or planned before signing of informed consent. However, unexpected complications and/or prolongation of hospitalization that occur during elective surgery should be recorded as adverse events and assessed for seriousness. Admission to the hospital for social or situational reasons (i.e., no place to stay, live too far away to come for hospital visits) will not be considered inpatient hospitalizations.

- A persistent or significant disability/incapacity or substantial disruption of the ability to conduct normal life functions;
- A congenital anomaly/birth defect; or
- An important medical event.

NOTE: Important medical events that may not result in death, be life-threatening, or require hospitalization may be considered an SAE when, based upon appropriate medical judgment, they may jeopardize the subject and may require medical or surgical intervention to prevent one of the outcomes listed in this definition. Examples of such medical events include allergic bronchospasm requiring intensive treatment in an emergency room or at home, blood dyscrasias or convulsions that do not result in inpatient hospitalizations, or the development of drug dependency or drug abuse.

9.3 Assessment of Adverse Events by the Investigator

9.3.1 Causality/Relatedness

The relationship of an adverse event to the administration of the study drug is to be assessed by the Investigator according to the following definitions:

Not Related (unlikely related, unrelated, not related, no relation) – The time course between the administration of study drug and the occurrence or worsening of the adverse event rules out a causal relationship and/or another cause (e.g., medical history, concomitant drugs, therapies, and complications) is suspected.

Related (possibly related, related) – The time course between the administration of study drug and the occurrence or worsening of the adverse event is consistent with a causal relationship and no other cause (e.g., medical history, concomitant drugs, therapies, and complications) can be identified.

The definition implies a reasonable possibility of a causal relationship between the event and the study drug. This means that there are facts (evidence) or arguments to suggest a causal relationship. The following factors should also be considered:

• The temporal sequence from study drug administration - The event should occur after the study drug is given. The length of time from study drug exposure to event should be evaluated in the clinical context of the event.

Protocol: BPN14770-CNS-203 Tetra Discovery Partners, Inc.
Date: 25 June 2018 Confidential

• Underlying, concomitant diseases (medical history) - Each report should be evaluated in the context of the natural history and course of the disease being treated and any other disease the subject may have.

- Concomitant drug The other drugs the subject is taking or the treatment the subject receives should be examined to determine whether any of them might be recognized to cause the event in question.
- Known response pattern for this class of study drug Clinical and/or preclinical data may indicate whether a particular response is likely to be a class effect.
- Exposure to physical and/or mental stresses The exposure to stress might induce adverse changes in the recipient and provide a logical and better explanation for the event.
- The pharmacology and PK of the study drug The known pharmacologic properties (absorption, distribution, metabolism, and excretion) of the study drug should be considered.

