6.2 Subject Inclusion Criteria

1. Subject is male aged 18 to 45 years, inclusive.

Protocol: BPN14770-CNS-203 Tetra Discovery Partners, Inc.
Date: 25 June 2018 Confidential

2. Subject has Fragile X Syndrome with a molecular genetic confirmation of the full Fragile X Mental Retardation (FMR1) mutation (≥200 CGG repetitions).

- 3. Current treatment with no more than 3 prescribed psychotropic medications. Anti-epileptic medications are permitted and are not counted as psychotropic medications if they are used for treatment of seizures. Anti-epileptics for other indications, such as the treatment of mood disorders, count towards the limit of permitted medications.
- 4. Permitted concomitant psychotropic medications must be at a stable dose and dosing regimen for at least 2 weeks prior to Screening and must remain stable during the period between Screening and the commencement of study medication.
- 5. Anti-epileptic medications must be at a stable dose and dosing regimen for 12 weeks prior to Screening and must remain stable during the period between Screening and the commencement of study medication.
- 6. Subjects with a history of seizure disorder who are currently receiving treatment with anti-epileptics must have been seizure-free for 3 months preceding Screening, or must be seizure-free for 3 years if not currently receiving anti-epileptics.
- 7. Behavioral and therapy treatments/interventions must be stable for 4 weeks prior to Screening and must remain stable during the period between Screening and the commencement of study medication, and throughout the study. Minor changes in hours or times of therapy that are not considered clinically significant will not be exclusionary. Changes in therapies provided through a school program, due to school vacations, are allowed.
- 8. Subject must be willing to practice barrier methods of contraception while on study, if sexually active. Abstinence is also considered a reasonable form of birth control in this study population.
- 9. Subject has a parent, legal authorized guardian or consistent caregiver.
- 10. Subject and caregiver are able to attend the clinic regularly and reliably.
- 11. Subject is able to swallow tablets and capsules.
- 12. For subjects who are not their own legal guardian, subject's parent/legal authorized guardian is able to understand and sign an informed consent form to participate in the study.

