9.3.3 Adverse Event Monitoring and Follow-up

Subjects who experience AEs will be monitored with relevant clinical assessments and laboratory tests, as determined by the Investigator. In accordance with good medical practice, all AEs must be followed to satisfactory resolution or stabilization of the event(s), or, if a chronic condition, until fully characterized. All follow-up results are to be reported to the Sponsor. Any actions taken and follow-up results must be recorded either on the appropriate page of the CRF or in a follow-up letter to the Sponsor, as well as in the subject's source documentation. Follow-up laboratory results should be filed with the subject's source documentation.

[figure not shown]
For all AEs that require the subject to be discontinued from the study, relevant clinical assessments and laboratory tests must be repeated at appropriate intervals until final resolution or stabilization of the event(s).

Subjects who have an ongoing SAE at study completion or study withdrawal must be followed until the event resolves or the event or sequela stabilizes. Subjects who have non-serious AEs that are ongoing at study completion or study withdrawal and are considered at least possibly

related to study treatment must be followed until resolution or for 30 days after the last dose of study drug, whichever comes first.

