9 SAFETY ANALYSES

9.1 Adverse Events

Adverse events will be coded using the Medical Dictionary for Regulatory Activities (MedDRA) coding system (using MedDRA version stated in Data Management Plan). An overall summary table will be presented by treatment group that summarizes all treatment-emergent adverse events, all serious treatment-emergent adverse events, all study drug-related treatment-emergent adverse events as assessed by PI, all study drug discontinuations due to treatment-emergent adverse events, number of deaths, and all severe treatment-emergent adverse events for the safety population. In addition, a frequency table will be presented by treatment group for all treatment-emergent adverse events by system organ class and preferred term for number and percentage of subjects:

- by maximum severity
- by relationship to study drug

An adverse event will be considered to be treatment-emergent for the treatment given in Period 1 if the event first appears after initial dosing in Period 1 or if it is a pre-existing condition that worsens following initial dosing through Period 2, Day 1. An adverse event will be considered to be treatment-emergent for the treatment given in Period 2 if the event first appears after Period 2, Day 1 or if it is a pre-existing condition worsens after Period 2, Day 1. Because the start time of adverse events is not collected on the case report form, it will be assumed that any TEAEs reported as starting on Period 2 Day 1 will be assigned to the treatment from Period 1. Any medical condition/event already present prior to the subject taking the first dose of study treatment will be reported in the medical history. Subject listings of all treatment-emergent adverse events will be provided.

In all displays, adverse events will be displayed by MedDRA System Organ Class and Preferred Terms, with subjects who have the same adverse event counted only once for that event and with subjects who have more than one adverse event within a System Organ Class counted only once

Version 1.0 16 July 2020

in that System Organ Class. An adverse event will be considered drug-related if, in the investigator's judgment, the event was related to treatment.

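### Protocol 9.3.1 gives conflicting tests for a drug-related adverse event, so related-event counts could be too low and inconsistently coded

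*Protocol*

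**What the plan says.** Protocol 9.3.1 has two causality categories.

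- The first is labelled "Related (possibly related, related", so possibly related events belong in it by name. It has two conditions joined by *and*: the timing must be compatible with the drug, and "no other cause (e.g., medical history, concomitant drugs, therapies, and complications) can be identified".
- The second, Not Related, has two triggers joined by *and/or*: the timing excludes the drug, or "another cause (e.g., medical history, concomitant drugs, therapies, and complications) is suspected". Either is enough alone.

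The text that follows sets a different test: "The definition implies a reasonable possibility of a causal relationship between the event and the study drug". It adds: "This means that there are facts (evidence) or arguments to suggest a causal relationship". It then lists matters to be taken into account, among them underlying disease, concomitant drugs, stress, the known pattern for the drug class, and pharmacology.

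The classification is used in several places. The overall table in SAP 9.1 includes "all study drug-related treatment-emergent adverse events as assessed by PI", and SAP 9.1 also tabulates events by relationship, as does Protocol 11.5. The SAP has no causality definition of its own and refers to the investigator's judgment. Protocol 9.3.3 applies a possibly-related threshold to non-serious events still ongoing when a subject finishes or leaves: events "related to study treatment must be followed until resolution or for 30 days after the last dose of study drug", with the earlier of the two points applying. Protocol 9.3.4 (new SAEs in the month after the study period) and 13.2 (prompt notification of the IRB) also use possibly related as their threshold.

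**The concern.** An event that fits the drug in time but also has another plausible explanation is what possibly related ordinarily means. The label puts it in Related, while the conditions beneath the label can keep it out. Two investigators who both follow 9.3.1 could code the same event in opposite ways.

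Such events can be expected in this trial. Protocol 6.2 allows "Current treatment with no more than 3 prescribed psychotropic medications" and does not count anti-epileptics used for seizures. Autism spectrum and anxiety diagnoses are allowed under 6.3. The events seen in earlier studies (nausea, vomiting, headache, diarrhoea, raised transaminases; Protocol 4.3.2) are not specific to one drug. Protocol 4.3.2.3 shows two drugs apparently contributing together: nausea and vomiting rose several fold when BPN14770 50 mg was added to scopolamine, compared with scopolamine alone. The definitions in 9.3.1 have no place for joint causation.

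Safety and tolerability is a stated objective, so the drug-related rows are a visible output of the trial.

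**Working it through.** No figure in the plan can be reproduced here. The check applies the definitions to each kind of event, then follows the result to where it is used.

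**1. Literal outcome for each kind of event**

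| Timing | Alternative cause | Meets Related? | Meets Not Related? |
|---|---|---|---|
| Excludes the drug | Any | No | Yes |
| Fits the drug | None suspected | Yes | No |
| Fits the drug | Suspected, not identified | Yes | Yes |
| Fits the drug | Identified | No | Yes |

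The third row is an overlap, because Related fails only on an *identified* cause while Not Related is met by a *suspected* one. The fourth row is an exclusion, taking an identified cause to be suspected as well.

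**2. The section's other test**

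Under the reasonable-possibility sentence, events in rows three and four can be Related whenever facts or arguments point to the drug. The two tests disagree for row four. For row three, the definitions do not decide.

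**3. Effect on the related count**

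Take the events that would be Related under the reasonable-possibility test. Let *a* be the share with an identified alternative, *b* the share with only a suspected one, and *f* the fraction of the *b* group coded Not Related.

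- Share recorded as related under the literal definitions: 1 − *a* − *f·b*.
- Understatement: *u* = *a* + *f·b*, which runs from *a* (*f* = 0) to *a* + *b* (*f* = 1).
- If the investigator follows the reasonable-possibility sentence throughout: *u* = 0.

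The documents give none of *a*, *b* or *f*. Any percentage only repeats what is assumed: assuming *u* between 10% and 50% gives a loss of 10% to 50%.

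**4. Effect on the treatment comparison**

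Assessment is blind (Protocol 7.4), so the same wording applies under BPN14770 and placebo. If *u* is the same under both, true counts *D* and *P* are recorded as (1 − *u*)*D* and (1 − *u*)*P*. The ratio stays at *D*/*P*, and the difference shrinks to (1 − *u*)(*D* − *P*). If *u* differs between treatments, the ratio moves too, in a direction the documents do not indicate. SAP 9.1 counts subjects, so this is approximate for its tables.

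**5. Effect on follow-up and reporting**

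- *Follow-up.* Protocol 9.3.3 also says that all adverse events are followed to resolution or stabilisation. Ongoing SAEs and events leading to discontinuation are followed whatever the relationship. Only the end-of-study sentence on ongoing non-serious events turns on relatedness.
- *SAEs to the sponsor.* Protocol 9.3.4 requires all SAEs to be notified up to 30 days after the last dose, whatever the relationship. With the last dose at the Period 2 Week 12 target (Day 84), that window ends on Day 84 + 30 = 114. A month of 30 days after the Week 13 contact (Day 91) ends on Day 91 + 30 = 121. The part that depends on relatedness is 121 − 114 = 7 days.
- *IRB.* Protocol 13.2 ties prompt notification to possibly related unexpected SAEs, but the same section separately lists serious and unexpected events for notification without that condition.

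**The case against.** The best defence is that 9.3.1 explains itself. The reasonable-possibility sentence says what the definition implies, alternatives are then listed as things to consider, and SAP 9.1 rests on the investigator's judgment. An investigator reading the section as a whole could code doubtful events as Related and lose none. There are also limits on how often an alternative would be credible. Three psychotropics is a ceiling, with no statement of typical use. Those drugs must have been stable for 2 weeks, and anti-epileptics for 12 weeks, before Screening. Under Protocol 9.1, worsening of a pre-existing condition is an adverse event only if it goes beyond the patient's usual variation.

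This stands against certainty and against any figure. It does not remove the conflict: the reader has to decide that the explanatory sentence overrides the explicit conditions, and the protocol does not say so.

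A reader might also infer that any suspected alternative automatically makes an event Not Related. The text does not support that, because such an event also satisfies Related. Nor do the documents show that most events would have an alternative cause, or that follow-up and late SAE reporting would be seriously curtailed, given the provisions that apply whatever the relationship.

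The timing objection has weight. SAP 8.1 refers to about two-thirds of subjects having already completed Period 1, so a change made then could mix two standards unless this is handled deliberately.

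**Conclusion.** The point holds as an internal inconsistency in Protocol 9.3.1. The definitions exclude well-timed events with an identified alternative cause and leave those with a suspected alternative in both categories. The label and the reasonable-possibility sentence call for weighing.

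Drug-related treatment-emergent counts could be understated and inconsistently coded under both treatments. The direction follows from the wording if the definitions are applied literally; the amount cannot be estimated from the documents. A reader might go further and say that the related table will lose a large, known share of events. That would need the proportion of events with an alternative cause and the investigators' coding practice, and neither is given.

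All-causality tables, including serious and severe events and discontinuations due to adverse events, are unaffected. Follow-up, late SAE reporting and IRB notification are touched only at the margin. The 7-day figure assumes last dosing on Day 84, a study end on Day 91 and a 30-day month.

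**What to change.** Reword the two definitions in Protocol 9.3.1 to agree with the section's own label and reasonable-possibility sentence. An alternative cause, suspected or identified, should be a factor to weigh and should not exclude an event automatically. No event should meet both definitions. Align the guidance for the adverse event form. SAP 9.1 needs at most a statement that the reconciled definition governs its drug-related tables.

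If the change comes after events have been coded, apply one standard to all of them, for example by blinded re-review of relatedness before unblinding.

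The wording change is about two sentences plus form guidance, with IRB approval of the amendment under Protocol 13.7. The costs are more events classed as related and, at a late stage, the re-review work.
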